## ELIGIBILITY ASSESSMENT AND ENROLLMENT

### 1.3 ELIGIBILITY CRITERIA

#### 1.3.1 Inclusion Criteria

1.3.1.1 Patients must have histologically or cytologically confirmed prostate cancer confirmed by the Laboratory of Pathology, NCI or Pathology Department at Walter Reed Bethesda.

1.3.1.2 Must have previously untreated (with definitive therapy) prostate cancer with intermediate or high risk features defined as:

**Intermediate risk:**

- PSA level is between 10 and 20 ng/ml or
- Gleason score is 7 or
- Stage T2b or T2c

**High Risk:**

- Gleason 8 and higher OR
- PSA > 20 at the time of diagnosis OR
- Seminal vesicle involvement OR
- Possible (on MRI) Extra-capsular extension (T3 disease)

1.3.1.3 Patients must be eligible for and must be planning to undergo radical prostatectomy

1.3.1.4 Patients must have testosterone levels  $\geq 100$  ng/dL

1.3.1.5 Men age  $\geq 18$  years.

Children are excluded because prostate cancer is not common in pediatric populations.

Women are not eligible because this disease occurs only in men.

1.3.1.6 ECOG performance status  $\leq 1$  (see APPENDIX A-Performance Status Criteria).

1.3.1.7 Patients must have normal organ and marrow function as defined below:

- Hemoglobin	$\geq 9$ g/dL
- leukocytes	$\geq 3,000/\text{mcL}$
- absolute neutrophil count	$\geq 1,500/\text{mcL}$
- platelets	$\geq 150,000/\text{mcL}$
- total bilirubin	within normal institutional limits
- AST(SGOT)/ALT(SGPT)	$\leq 3$ X institutional upper limit of normal
- creatinine	within normal institutional limits
OR	
- creatinine clearance	$\geq 60$ mL/min/1.73 $\text{m}^2$ for patients with creatinine levels above institutional normal. (calculated via Cockcroft-Gault equation)

1.3.1.8 The effects of enzalutamide on the developing human fetus are unknown. For this reason and because androgen receptor antagonists as well as other therapeutic agents used in this trial are known to be teratogenic, male participants and their female partners of child bearing potential must agree to use adequate contraception (hormonal or barrier method of birth control; abstinence). Male participants should use a condom if having intercourse with a pregnant woman. Additionally, a condom plus another effective method of birth control is recommended during therapy and for 3 months after treatment for male participants having intercourse with a woman of reproductive potential. Should a woman become pregnant or suspect she is pregnant while her partner is participating in this study, she should inform her treating physician immediately.

1.3.1.9 Ability of subject to understand and the willingness to sign a written informed consent document.

1.3.1.10 Willingness to undergo biopsy.

1.3.1.11 Ability to detect lesions within prostate on MRI for biopsy

1.3.1.12 Willingness to travel to NIH for follow-up visits.

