## INTRODUCTION

### 1.1 STUDY OBJECTIVES

#### 1.1.1 Primary Objective

- To test the feasibility of mpMRI for the localization and detection of focal prostate cancer both before and after pre-operative treatment with ADT and enzalutamide.

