Figure 2: Customized, patient-specific prostate specimen mold. (a)Three-dimensional representation of final prostate mold in green, shown in two halves with a 3D model of the patient's prostate shown in brown. (b) Mold is created using a 3D printer, shown here in two halves fit together using small pegs/slots in the corners.

The mold approach has also been shown to allow for decision system support development [\[24\]](#) that provides a probability map of peripheral zone cancers based upon MRI. This expertise will be critical to the imaging, allowing suspicious lesions to be targeted for biopsy and subsequent correlative genetic analyses to be performed on the tissue from the index lesion(s). This unique tool allows for the most accurate alignment of the prostate specimen to MR images that is available today. This resource available here at the NCI will be essential for the success of this proposal allowing for precise validation of in vivo imaging studies by enabling registration for focal lesion core biopsy and whole mount histopathology.

Figure 3: Digitized multiparametric MRI maps (left) and the corresponding digitized whole-mount histopathology (right) slice with tumor outlined by a prostate cancer pathologist, and used as a landmark for lesion confirmation on mp MRI maps determine lesion localization.

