## **STATISTICAL CONSIDERATIONS**

The primary objective of this exploratory trial is to obtain pilot data to assess the utility and role of mpMRI in localization and detection of focal prostate cancer both before and after treatment with pre-operative ADT and enzalutamide. Secondary objectives include obtaining pilot data to guide future studies with respect to determining genetic predictors and correlates of response to therapy as well as to link imaging information to genomic information related to resistance.

Patients who have newly diagnosed prostate cancer will undergo treatment with androgen deprivation therapy and enzalutamide and will undergo mpMRI imaging at screening and 6 months. The imaging will be used to monitor the changes in the individual tumors located within the prostate. As these patients will all have multiple tumors within the prostate, it is anticipated that approximately 25% of the patients will experience minimal declines in tumor and still have significant residual disease, 25% may have complete disappearance of tumor, and the remainder will show substantial improvement (disappearance of some lesions, with others being much smaller). To guide sample size determination, it is estimated that for an exploratory investigation of the association of genomic information and its relationship to response, it would be useful to have at least a minimum of 10 patients who still have significant residual disease in order to form preliminary assessments of the relationships noted. As such, if 50 total evaluable patients were to enroll on the trial and if the probability of being in this category was 25%, there would be 83.6% probability of having at least 10 such patients. Thus, this pilot study will plan to enroll 50 total evaluable patients who would all undergo primary treatment and mpMRI imaging to assess the role of imaging in this setting. The accrual ceiling will be 55 in order to accommodate a small number of patients who may be inevaluable. Successful use of this imaging will lead to analyses related to the association with genomic traits at baseline and prostatectomy and whether there is disappearance of tumor or not. On this trial, all of these investigations will be performed with exploratory, hypothesis generating intent.

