## **REGULATORY AND OPERATIONAL CONSIDERATIONS**

### **1.32 STUDY DISCONTINUATION AND CLOSURE**

This study may be temporarily suspended or prematurely terminated if there is sufficient reasonable cause. Written notification, documenting the reason for study suspension or termination, will be provided by the suspending or terminating party to study participants. If the study is prematurely terminated or suspended, the Principal Investigator (PI) will promptly inform study participants and the Institutional Review Board (IRB) and will provide the reason(s) for the termination or suspension. Study participants will be contacted, as applicable, and be informed of changes to study visit schedule.

Circumstances that may warrant termination or suspension include, but are not limited to:

- Determination of unexpected, significant, or unacceptable risk to participants
- Demonstration of efficacy that would warrant stopping
- Insufficient compliance to protocol requirements
- Data that are not sufficiently complete and/or evaluable
- Determination that the primary endpoint has been met

- Determination of futility

Study may resume once concerns about safety, protocol compliance, and data quality are addressed, and satisfy the IRB.

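### Does the plan need to define successful imaging and name a reference standard for the pre-treatment mpMRI?

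*Combined protocol and SAP*

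**What the plan says.** Section 1.1.1 sets the primary objective as the feasibility of mpMRI for "localization and detection of focal prostate cancer both before and after pre-operative treatment with ADT and enzalutamide". Entry requires a lesion visible on MRI as a biopsy target ("Ability to detect lesions within prostate on MRI for biopsy", 1.3.1.11) and proven disease ("Patients must have histologically or cytologically confirmed prostate cancer", 1.3.1.1).

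Statistical Considerations plans 50 evaluable men. It expects about 25% to keep significant residual disease, says that "25% may have complete disappearance of tumor", and describes the rest as improving substantially ("disappearance of some lesions, with others being much smaller"). On the link to genomics it says "Successful use of this imaging will lead to analyses related to the association with genomic traits at baseline and prostatectomy". It closes by calling all the investigations exploratory and hypothesis generating.

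Two other places touch the point. Section 1.2.6 describes the patient-specific mold as "allowing for precise validation of in vivo imaging studies by enabling registration for focal lesion core biopsy and whole mount histopathology". Section 1.32 includes "Determination that the primary endpoint has been met" among the circumstances that may justify stopping. No section states a primary endpoint, a feasibility threshold, or a reference standard labeled for each scan.

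**The concern.** Half of the primary objective concerns the first scan, and its result depends on what it is compared with.

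- **A visible lesion.** All men have one, because they could not enter without it. The figure says nothing about the scan.
- **A positive targeted core.** The targeted biopsy is a screening procedure and confirmed cancer is an entry condition. If that biopsy supplied the qualifying pathology, each man has at least one positive target by rule and the rate is biased upward. The documents do not say which biopsy qualifies a man.
- **The prostatectomy specimen.** It is removed after therapy that the plan expects to clear tumor in some men, so a true baseline lesion may no longer be there.
- **Sensitivity.** The pre-treatment cores described come from MRI index lesions. They inform positive predictive value (PPV), not the share of cancers found.

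If the genomic association analyses depended on success, and success could be chosen among these readings after the data were seen, the pilot's main conclusion would be open to selection.

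**Working it through.** **1. The plan's own figure.** With n = 50 and p = 0.25, the exact binomial gives P(X ≥ 10) = 0.8363, which matches the stated 83.6%. It concerns having enough men with residual disease for the genomic work. It does not involve imaging success, so leaving success undefined does not affect it.

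**2. Does anything depend on success?** The sentence in Statistical Considerations reads like a condition. Set beside it:
- The Précis (Design) has all tumor specimens analyzed genomically.
- Section 1.1.2 lists sequencing as a secondary objective with no imaging condition.
- Section 1.8 sends both screening biopsies and prostatectomy tissue for genomic analysis, subject to consent.
- Section 1.20 says there is no formal radiographic assessment of response.

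No hypothesis test, threshold or interim rule uses the term. The list in Section 1.32 is expressly open-ended and generic. It also names a demonstration of efficacy, though this single-arm pilot has no efficacy test.

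**3. Is the reference tissue really open?** The table in Section 1.17.1 pairs the first MRI with in vivo biopsy of the index lesions, and the second with prostatectomy and ex vivo biopsy of the same lesions. The text there uses the pre-treatment core to confirm diagnosis, grade and extent. It uses the specimen to look for residual tumor and to compare MRI with pathologic response. Neither is labeled a reference standard, but the natural pairing is clear. No section scores the first scan against the specimen.

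**4. How low could the first scan look if it were scored that way?** Suppose a perfect baseline scan, equal lesion counts per man, and disappearance that is pathological.

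- By men: 1 − 0.25 = 75% still have tumor, and 0.75 × 50 = 37.5, so about 37 of 50.
- By lesions: share confirmed = 1 − (0.25 + 0.50x), where x is the share of lesions vanishing in the partly responding half.

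The plan says that in that half some lesions vanish and others remain. With 2 or 3 lesions per man, at least one lost and one kept, x runs from 1/3 to 2/3 (assumed):

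| x | PPV 100% | PPV 98% (cited in 1.2.5) |
|---|---|---|
| 1/3 | 1 − 0.417 = 58% | 57% |
| 2/3 | 1 − 0.583 = 42% | 41% |

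If only half of the lesions counted as cleared are truly free of tumor, the perfect-scan figures become 1 − 0.5 × 0.417 = 79% and 1 − 0.5 × 0.583 = 71%.

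An extreme reading gives 0.70 × 0.25 = 17.5% of lesions. It needs a 70% PPV that is not in the documents, and x = 1. At x = 1, 25% + 50% = 75% of men would have complete disappearance, against the plan's 25%. It also counts lesions, so it cannot be set beside 100% of men.

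**5. Size of the selection bias in targeted cores.** If the same biopsy qualified the man, the expected share of positive targets is p / (1 − P0), where P0 is the chance of no positive target (beta-binomial). At an assumed p = 0.70, 2 or 3 lesions per man and within-man correlation 0.1 to 0.5, this is 73.5% to 87.0%; with one lesion it is 100%. At the cited 98% it lies between 98% and 100%, a bias of at most two percentage points. If an earlier biopsy qualified the man, this bias does not arise.

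**The case for a change.** The best argument for a change is that an exploratory label lowers the stakes without saying what is to be measured. A pilot meant to judge the role of mpMRI should fix its measure beforehand, and a few sentences would do that at no cost in patients or tissue. If the sentence about genomics is only narrative, one line could say so.

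Part of this stands. Success is undefined. The share of men with a visible baseline lesion is uninformative. Targeted cores cannot give sensitivity, and absence of tumor after treatment cannot show that a baseline lesion was false. Any report has to respect these limits.

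The rest is weaker. A visible lesion is not a confirmed cancer, so Section 1.3.1.11 does not by itself meet half of an objective about detecting cancer. The rule is also needed, because paired sampling requires a target. Proposals that go beyond writing a definition are matters of preference: resting accuracy on the second scan alone, or barring any comparison of detection before and after, would narrow an objective that names both scans. Whole-mount histology is not assured for every man either, since Section 1.17.1 says the specimen can be sectioned that way and also describes cutting sections into halves or quadrants. Whether off-target cores exist, and which biopsy qualified each man, depends on screening protocol 01-C-0129, which is not among these documents.

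**Conclusion.** No change is needed. The plan omits a definition, but it states no rule that would give a wrong result, and nothing confirmatory rests on the missing term. An analyst would read the first scan against the targeted cores and the second against the prostatectomy specimen, as the table in Section 1.17.1 lays out. Baseline findings would be described as those of men selected for MRI-visible lesions, and lesions treated away would not be counted as false positives.

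The large spread between readings comes mainly from scoring the first scan against post-treatment tissue, which the plan does not propose. On the plan's own expectations that would confirm about 75% of men for a perfect scan, or about 42% to 58% of lesions. These figures assume pathological disappearance and equal lesion counts; the lesion range also assumes x between 1/3 and 2/3. The sample size of 50 and its 83.6% are unaffected. The judgment rests on the genomic work being unconditional, as the Précis, Section 1.1.2 and Section 1.8 indicate, and on the declared exploratory intent.

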### **1.3.2 Exclusion Criteria**

1.3.2.1 Patients who are receiving any other investigational agents (in the past 28 days) or herbal medications (within 1 day).

1.3.2.2 Patients with distant metastatic disease beyond N1 (regional) lymph nodes on conventional imaging studies (CT, MRI or Bone Scan).

1.3.2.3 Patients who have received any prior therapy for prostate cancer with surgery, radiation, and/or chemotherapy

1.3.2.4 History of allergic reactions attributed to compounds of similar chemical or biologic composition to enzalutamide or other agents used in study.

1.3.2.5 Clinically significant cardiac disease, e.g., New York Heart Association (NYHA) classes III-IV; uncontrolled angina, uncontrolled arrhythmia or uncontrolled hypertension, myocardial infarction in the previous 6 months as confirmed by an electrocardiogram (ECG).

1.3.2.6 Contraindication to biopsy:

- Bleeding disorders
- PT/PTT  $\geq$  1.5 times the upper limit of normal
- Artificial heart valve

1.3.2.7 Contraindication to MRI:

- Patients weighing more than weight limit for the scanner tables
- Allergy to MR contrast agent
- Patients with pacemakers, cerebral aneurysm clips, shrapnel injury or implantable electronic device

1.3.2.8 Uncontrolled intercurrent illness including, but not limited to, ongoing or active infection, symptomatic congestive heart failure, unstable angina pectoris, cardiac arrhythmia, or psychiatric illness/social situations that would limit compliance with study requirements.

1.3.2.9 Patients with known HIV are ineligible. These patients are at increased risk of lethal infections when treated with marrow-suppressive therapy. In addition, if patients are receiving combination antiretroviral therapy, there is potential for pharmacokinetic interactions with enzalutamide. Appropriate studies will be undertaken in patients receiving combination antiretroviral therapy when indicated.

1.3.2.10 Patients with known active treatment for Hepatitis B and C infections.

1.3.2.11 Patients who are taking medications that are strong inhibitors of CYP3A4 or PgP and need to remain on these medications. For a current table of Substrates, Inhibitors and Inducers please access the following website:

**Abbreviated Title:** Neoadjuvant ADT & Enzalutamide

**Version Date:** 01/25/2024

<http://www.fda.gov/Drugs/DevelopmentApprovalProcess/DevelopmentResources/DrugInteractionsLabeling/ucm093664.htm>

- 1.3.2.12 History of seizure, including any febrile seizure, loss of consciousness, or transient ischemic attack, or any condition that may pre-dispose to seizure (e.g., prior stroke, brain arteriovenous malformation, head trauma with loss of consciousness requiring hospitalization).
- 1.3.2.13 Other medications used for urinary symptoms including 5-alpha reductase inhibitors (finasteride and dutasteride) and alternative medications known to alter PSA (e.g., phytoestrogens and saw palmetto) cannot be taken while patients are receiving enzalutamide
- 1.3.2.14 Patients with a malignancy within the past 3 years for which study drugs or a prostatectomy is a contraindication.

### 1.3.3 Recruitment Strategies

This protocol may be abstracted into a plain language announcement posted on NIH websites and on NIH social media platforms.

## 1.4 SCREENING EVALUATION

### 1.4.1 Screening activities performed after a consent for screening has been signed

Screening evaluation testing/procedures are conducted under the separate screening protocol, 01-C-0129 (Eligibility Screening and Tissue Procurement for the NIH Intramural Research Program Clinical Protocols).

- **Pathological confirmation** of malignancy by the Laboratory of Pathology, NCI or Pathology Department at Walter Reed National Military Medical Center.
- **Within 12 weeks** of study entry: Bone scan, CT and/or MRI scans as appropriate for disease evaluation.
- **Within 8 weeks** of study entry: ECG, laboratory tests: CBC with differential and platelet count, Creatinine, ALT, AST, total bilirubin, PT/PTT, serum PSA, testosterone level, focused history, physical examination with documentation of weight, measurable disease and performance status.
- **Within 6 months** of study entry: 3T mpMRI and U/S Guided Targeted Biopsy of the prostate

For baseline evaluations, please see Section [2.5](#).

## 1.5 PARTICIPANT REGISTRATION AND STATUS UPDATE PROCEDURES

Registration and status updates (e.g., when a participant is taken off protocol therapy and when a participant is taken off-study) will take place per CCR SOP ADCR-2, CCR Participant Registration & Status Updates found at:

<https://ccrod.cancer.gov/confluence/pages/viewpage.action?pageId=73203825>.

**Abbreviated Title:** Neoadjuvant ADT & Enzalutamide

**Version Date:** 01/25/2024

## 1.6 TREATMENT ASSIGNMENT PROCEDURES

### Cohort

Number	Name	Description
1	Cohort 1	Men $\geq$ 18 years old with non-metastatic prostate cancer

### Arm

Number	Name	Description
1	Arm 1	Patients will have an mpMRI guided biopsy, then receive enzalutamide and goserelin treatment for 6 months followed by a second mpMRI examination.

## 1.7 BASELINE EVALUATION

- History and physical examination within 17 days of treatment initiation (for medical record only).
- Laboratory and urine studies (Tests completed at screening may be omitted if performed *within 17 days* of treatment initiation): **CBC with differential** and platelet count, **PT/PTT**, and **Acute care panel** (Serum sodium, Potassium test, Serum chloride, CO2, Creatinine, Glucose test, BUN); **Mineral panel** (Albumin, Calcium, Magnesium, Phosphorus – serum); **Hepatic Panel** (Alkaline phosphatase, ALT, AST, direct and total bilirubin); Gamma-GT, LDH, total cholesterol, total protein, Serum PSA, uric acid, urinalysis
- Baseline ECG (within 17 days of treatment initiation)
- Vital signs including weight and height.

## STUDY IMPLEMENTATION

### 1.8 STUDY DESIGN

All men (n=50) enrolled in the trial will undergo two 3T mpMRI endorectal examinations, one at screening before treatment and a second after completing 6 months of goserelin and enzalutamide just prior to surgery. Radical Prostatectomy will be performed as per standard procedures at either the Clinical Center or Walter Reed Bethesda. Screening biopsy (MR/US guided) samples and tissue from the prostatectomy specimens will all undergo pathologic and genomic analysis. Genomic analysis will only be performed after obtaining informed consent. Genomic analysis will involve parallel sequencing and evaluation of molecular resistance mechanisms. We will obtain one or two cores from each index lesion(s)-up to 3 index lesions will be identified per patient and record all the needle locations. One core from each index lesion will undergo both routine pathologic examination as well as genetic analysis. Patients will be treated prior to surgery with standard doses of goserelin and enzalutamide. It is anticipated that different patients and conceivably different lesions within a patient may have differential responses to treatment by mpMRI. Genomic analysis will be performed from areas of

[figure not shown]
**Abbreviated Title:** Neoadjuvant ADT & Enzalutamide

**Version Date:** 01/25/2024

pathologically confirmed and MRI identified unresponsive areas of tumor within the same patient. In addition, using a whole-mount prostate mold, the same areas identified as were biopsied at screening (e.g., dominant lesion identified on mpMRI) can be directly re-biopsied for comparative genomic analysis.

